**Subject Information**

**Target accrual:** We plan to recruit 40 Mayo Clinic Practicing HCP.

**Subject population:** A total of 40 practicing HCP at Mayo Clinic who meet the following study criteria:

**Inclusion Criteria:**

1. 18 years of age or older at time of consent
2. Practicing HCP at Mayo Clinic
3. Not pregnant by subject self-report at time of consent
4. Have the ability to provide informed consent
5. Have the ability to complete all aspects of this trial
6. Have access to an iPhone, iPad, or Android device
7. Have no contraindicating comorbid health condition which would interfere with the proper use of the Muse-S™ system, as determined by the clinical investigators

**Exclusion Criteria:**

1. Used an investigational drug within the past 30 days
2. Anyone that is not on a stable dose of medication for anxiety, depression or sleep
3. Currently (within the past 3 weeks) been practicing mindfulness training on a weekly/regular basis
4. Currently (within 3 weeks) has been enrolled in another clinical or research program which intervenes on the patients' QOL, or stress
5. An unstable medical or mental health condition as determined by the physician investigator

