#### Recruitment:

HCP participants will be recruited from the Mayo Clinic Practice. The study staff will inform participants of the study during practice meetings, and if the participants indicate interest they will connect with research staff and arrange a time to meet to begin the consent process.

Participants will not be reimbursed for their time spent in the study, but all participants will be given the option of keeping the Muse-S™ Headband system for continued use post study participation.

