General Study Information

Principal Investigator: [name]

A Study Title: A Feasibility study evaluating Mindfulness-Based Intervention Assessing A Wearable Wellness Brain Sensing Device (Muse-S™) in Practicing Health Care Providers.

Protocol date: 23 Sept 2024

Data Analysis

Data Analysis Plan:

Demographic characteristics are described using mean and standard deviations or frequencies and percentages based on the type of variable. For the primary aim of assessing feasibility, descriptive statistics and graphical displays will be presented for data obtained on frequency and duration of use over the 12 weeks of treatment. A linear mixed model with repeated measures for each time point that stress and sleep were taken will be utilized to estimate the association between the average of time spent using the Muse-S™ with the stress and sleep level outcome. Age, sex, and the total amount of meditation time at each interval will also be adjusted for in the model. As secondary outcomes, the results of the LASA, resilience, coping, and cognitive testing will be analyzed using linear mixed models with repeated measures to determine changes over time. In all cases, results will be summarized using point-estimates and corresponding 95% confidence intervals. Given the number of outcomes assessed, all analyses will be considered exploratory.

Endpoints:

Primary Hypothesis:

- a) HCP enrolled in this study will find the Muse-S™ Headband system easy to use and will use it often during the work week.

Secondary Hypotheses:

- a) Stress score will be lower and sleep score will be improved when compared to the baseline measures for those who use the Muse-S™ system as directed.
- b) As the use of the Muse-S™ system increases, QOL, resilience and coping will improve.

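### Exclusion criterion 2 lacks an 'if taking' condition, so read literally it shuts out every HCP who takes no anxiety, depression or sleep medicine, against the general-HCP scope of the trial

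*Protocol*

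**What the plan says.** Item 2 of the protocol's Exclusion Criteria reads "Anyone that is not on a stable dose of medication for anxiety, depression or sleep". Item 5 of the same list reads "An unstable medical or mental health condition as determined by the physician investigator".

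The population is described elsewhere as follows:

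- Subject Information, target accrual: "We plan to recruit 40 Mayo Clinic Practicing HCP".
- Subject Information, subject population: "A total of 40 practicing HCP at Mayo Clinic who meet the following study criteria".
- Inclusion Criteria, item 2: "Practicing HCP at Mayo Clinic". None of the seven inclusion items asks for any medication.
- Recruitment: "HCP participants will be recruited from the Mayo Clinic Practice", with the study announced at practice meetings.

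The Hypothesis section argues from the stress of caring for patients during the pandemic and treats providers as one group. The SAP title likewise names practicing health care providers without qualification. Under Consent and Screen, the coordinator checks each consenting person against the inclusion and exclusion lists, and only those who meet them start the study.

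**The concern.** The item is phrased as a negative with no condition attached. It excludes people who lack something (a stable dose), when the apparent aim is to exclude people who have something (a changing dose). A provider who takes none of these medicines lacks a stable dose and so meets the exclusion as written.

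Two things are at stake. First, this is an operative screening rule. Two coordinators could apply it to the same unmedicated provider and reach opposite answers, each with a defensible reading. Second, a reader of the results cannot tell from the protocol whether they describe providers in general or only those on stable medication. That matters for the outcomes chosen: stress and sleep are both modelled, and the sleep index counts use of sleep medication as one of its seven components.

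**Working it through.** The plan has no figure to reproduce on this point. The target of 40 is stated without a derivation and is not in dispute. The check is a comparison of readings and then of sections.

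**Step 1. Apply the item to each type of person** (for simplicity, someone who takes at most one such medicine):

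| Person | Literal reading | Reading limited to people on medication |
|---|---|---|
| Takes such a medicine, dose stable | Not excluded | Not excluded |
| Takes such a medicine, dose not stable | Excluded | Excluded |
| Takes no such medicine | **Excluded** | **Not excluded** |

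The readings differ only in the third row, but there they give opposite answers for the whole group.

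**Step 2. Look for text that settles the third row.** Neither document adds a condition such as 'if taking'. Neither says that unmedicated providers are eligible, and neither says that they are not.

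**Step 3. Compare with the described scope.** The Hypothesis, Recruitment and Inclusion Criteria sections and the SAP title all refer to providers generally. A trial meant only for people on stable psychotropic or sleep medication would be expected to say so in at least one of these places. Item 5 of the exclusion list is aimed at instability of a condition, which suggests that item 2 is aimed at instability of dosing. This is an inference; the documents do not state it.

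**Step 4. Can the effect be sized?** Let *s* be the share of otherwise eligible providers who are on a stable dose. Under the literal rule the pool shrinks to *s* of its size, and enrolling 40 needs about 40/*s* otherwise eligible people. The documents do not give *s*. Purely assumed values give:

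- *s* = 10%: 40/0.10 = 400
- *s* = 20%: 40/0.20 = 200
- *s* = 50%: 40/0.50 = 80

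The spread comes entirely from the assumption, so none of these is a finding. What does not depend on *s* is that the literal rule removes every unmedicated provider.

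**Step 5. Check for knock-on effects in the SAP.** The primary analysis is descriptive, and the SAP says "Given the number of outcomes assessed, all analyses will be considered exploratory". No power calculation, error rate or estimator depends on item 2.

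**The case against.** The best defence is that nobody would read the item this way. To speak of not being on a stable dose ordinarily presupposes that a dose is being taken, item 5 points in the same direction, and staff recruiting at general practice meetings are unlikely to turn away every unmedicated colleague. Concomitant medication is also recorded from baseline, so the medication status of those enrolled can be reported. All of this stands, and it is why the point is minor. It does not remove the point: an exclusion criterion should not need the screener to supply its missing condition.

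Several stronger readings are tempting, and the documents do not support them:

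- *The item contradicts the stated population.* Subject Information defines the population as providers who meet the listed criteria, so the exclusions are part of the definition. A restrictive item narrows that population without formally contradicting it. The conflict is with the general scope described elsewhere.
- *Unmedicated participants would be dropped from an analysis set.* The SAP defines no eligible-only or per-protocol set.
- *Every unmedicated participant would be a recorded violation.* If staff screen by intent, these people are eligible and nothing is recorded. Someone later applying the literal text might query them, which is a weaker claim.
- *Most of the 40 would be ineligible.* Any such count rests on an assumed share of staff on medication. It would also have to use the share on a stable dose, which is not the same as the share taking medication.

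**Conclusion.** The point holds as a low-severity error in eligibility wording. As written, item 2 excludes all providers who take no medicine of these three kinds. No other text corrects it, and the result is at odds with the general-provider scope of the rest of the protocol and the SAP title. The practical risk is inconsistent screening and doubt about whom the results describe.

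The size cannot be stated, because the share of providers affected is not given. Sample size, power, endpoints and estimators are untouched. The conclusion about literal meaning needs no assumption. The view that the sponsor meant only to exclude changing doses is a likely inference, so the sponsor should confirm it.

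**What to change.** Reword item 2 so that it applies only to people who currently take a medicine of one of these three kinds and whose dose is not stable. Have the sponsor state explicitly whether providers who take none are eligible, and reconcile the item with the Recruitment, Subject Information and Inclusion Criteria sections. The definition of stable is for the investigators to set.

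The cost is one sentence in an amendment. If screening already follows the evident intent, conduct does not change.

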**Review of medical records, images, specimens**

The study involves data that exist at the time of IRB submission **and** data that will be generated after IRB submission. Include this activity in the Methods section.

General Study Information

Principal Investigator: [name]

A Study Title: A Feasibility study evaluating Mindfulness-Based Intervention Assessing A Wearable Wellness Brain Sensing Device (Muse-S™) in Practicing Health Care Providers.

Protocol date: 23 Sept 2024

Data Analysis

Data Analysis Plan:

Demographic characteristics are described using mean and standard deviations or frequencies and percentages based on the type of variable. For the primary aim of assessing feasibility, descriptive statistics and graphical displays will be presented for data obtained on frequency and duration of use over the 12 weeks of treatment. A linear mixed model with repeated measures for each time point that stress and sleep were taken will be utilized to estimate the association between the average of time spent using the Muse-S™ with the stress and sleep level outcome. Age, sex, and the total amount of meditation time at each interval will also be adjusted for in the model. As secondary outcomes, the results of the LASA, resilience, coping, and cognitive testing will be analyzed using linear mixed models with repeated measures to determine changes over time. In all cases, results will be summarized using point-estimates and corresponding 95% confidence intervals. Given the number of outcomes assessed, all analyses will be considered exploratory.

Endpoints:

Primary Hypothesis:

- a) HCP enrolled in this study will find the Muse-S™ Headband system easy to use and will use it often during the work week.

Secondary Hypotheses:

- a) Stress score will be lower and sleep score will be improved when compared to the baseline measures for those who use the Muse-S™ system as directed.
- b) As the use of the Muse-S™ system increases, QOL, resilience and coping will improve.

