**Study Design and Methods**

**Methods:**

All study participants will receive the Muse S™ Headband system at study entry and will be asked to utilize it at least 4 times per week for a minimum of 10 minutes each time over a period of 3 months (12 weeks). They will be followed for a period of 6 months (3 months of treatment and 3 months post treatment) according to the schedule below.

We will assess the following:

- Type of meditation the patient has selected from the 3 available options: Mind Meditation, Guided Meditation and Go-to-sleep meditation.
- Frequency and duration of use from baseline to month 3 (end of treatment). The participants will be informed at baseline that for best results, it will be recommended that they use it a minimum of 10 minutes, at least 4 times per week for over 3 months. If they are short on time, they can break up the 10 minutes and do shorter meditations.

- Changes in QOL, stress, resilience, and sleep score from baseline through week 2, month 1, month 3 and month 6.

Visit No.	Consent /screen /baseline	Treatment Phase			Follow up Phase
	1	2	3	4	5
Visit Type	face to face	Phone/ email	Phone/ email	face to face/phone/ email	face to face/phone/ email
Visit Days	0	14	30	90	180
Informed Consent	X				
Inclusion/Exclusion	X				
Demographic and History Form	X				
Depression	X	X	X	X	X
Burnout	X			X	X
Resilience	X	X	X	X	X
Sleep	X	X	X	X	X
Quality of Life	X	X	X	X	X
Stress Scale	X	X	X	X	X
Satisfaction Survey					X
Adverse Events 		X	X	X	X
CBS Cognitive Tests	X			X	X
Concomitant Medication 	X	X	X	X	X
Instructions for Muse-S™	X				
End of Treatment/End of Study Forms				X	X

1 = For visit 5, only serious adverse events will be newly collected; 2 = For visit 5, only newly added concomitant medications will be collected

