- **Satisfaction with the program:** This questionnaire is adapted from *Was it Worth it Questionnaire (WIWI)* to measure study and Muse-S™ satisfaction. It will be administered to the participants after completing the intervention at the end of the study, probing their satisfaction with the research study. These data could be used to assess the feasibility of the intervention by asking the patient if the entire research experience was worth it for them.

*Adherence to Intervention:*

- **Adherence to the Muse-S™** will be assessed by de-identified data available within the cloud, provided by InteraXon. InteraXon only has information per subject through subject ID only (as was provided by Mayo Clinic site), so when the cloud data is provided to Mayo, it will be linked to each subject through their study ID.

*Intervention:*

- **The Muse-S™ Headband system:** The Muse-S™ Headband system is a brain sensing headband that measures brain activity by detecting electrical impulses created by the brain. The Muse-S™ Headband system uses a series of focus attention training methods to train the brain. Each focus attention session can vary in length, with the ideal being a minimum of 10 minutes, and has been shown to reduce stress, anxiety, and improve focus and productivity. The Muse-S™ Headband system has seven sensors with four channels of EEG data for an accurate, high-quality experience. The battery life is approximately five hours and uses an industry-standard micro-USB charger. Twenty Muse-S™ Headband systems will be provided by the manufacturer at no cost in support of this study.

[figure not shown]
Use of Muse-S™ Headband systems will be demonstrated to each participant prior to their first mindfulness practice session, which will be completed during the baseline visit with the study coordinator. The study coordinator will present the participant with detailed instructions on how to begin each session. The frequency of the sessions thereafter will be at the participant’s discretion according to the study’s requirements (daily practice). Mindfulness training will follow the protocol in the Muse-S™ APP, which follows a standard breathing exercise with EEG brain state feedback through the mobile device, as designed by a panel of experienced mindfulness practitioners. In short, the Muse-S™ is a *FitBit* like device for the brain.

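### The stress and sleep model relates score levels to self-chosen average use with no baseline, change or use-by-time term, so stable entry differences between heavier and lighter users pass into the use coefficient

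*SAP*

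**What the plan says.** The study has a single arm: "All study participants will receive the Muse S™ Headband system at study entry" (Protocol, Study Design and Methods). Participants are asked to meet a weekly minimum, but the Protocol's description of the intervention adds: "The frequency of the sessions thereafter will be at the participant’s discretion". The accrual target is 40 (Protocol, Subject Information).

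Stress and sleep are scheduled at Days 0, 14, 30, 90 and 180. The schedule row for stress reads "Stress Scale X X X X X", and the sleep row has the same five marks. The Methods list "Changes in QOL, stress, resilience, and sleep score from baseline through week 2, month 1, month 3 and month 6" among the assessments.

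For stress and sleep the SAP writes: "A linear mixed model with repeated measures for each time point that stress and sleep were taken will be utilized to estimate the association". The predictor is average use of the device over an unstated period, and the outcome is the level of each score rather than its change. On covariates the SAP says: "Age, sex, and the total amount of meditation time at each interval will also be adjusted for in the model". No baseline score, change score or use-by-time term is named. The SAP specifies analysis of change over time only for the LASA, resilience, coping and cognitive tests.

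Secondary hypothesis (a) in the SAP, however, is that stress and sleep improve relative to baseline in those who use the device as directed. The Protocol also lists change in stress over time as a secondary outcome.

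**The concern.** Heavier and lighter users are self-selected. If less stressed or less busy providers find more time to meditate, heavier users have lower stress scores at every visit, including Day 0. If stressed providers turn to the device for relief, the reverse holds. A model of score levels with one average-use value per person cannot separate either pattern from an effect of use. With no term that lets the use slope differ between Day 0 and later visits, the coefficient reports the entry difference along with anything that happened afterwards.

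This is the only model in the SAP that names use as a predictor of an outcome. A reported slope of stress on use, with its 95% confidence interval, could be read as a dose-response relation when it only shows who chose to use the device. The model also does not deliver the comparison with baseline that the plan sets out to make.

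**Working it through.** The documents give no SD, effect size, power or precision figure for this model, so there is no plan figure to reproduce.

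**Inputs**
- From the documents: 40 participants; visits at Days 0, 14, 30, 90 and 180; covariates age, sex and interval meditation time; stress scale 0 to 40.
- Assumed: stress-score SD 6; within-person correlation ρ = 0.5 to 0.7; correlation r between average use and a participant's stable stress level of 0, −0.3 or −0.5; true effect of use zero.

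**Level model, closed form.** Spurious slope per SD of use: c = r × SD × √ρ.
- r = −0.3, ρ = 0.5: −0.3 × 6 × 0.707 = −1.27
- r = −0.3, ρ = 0.7: −0.3 × 6 × 0.837 = −1.51
- r = −0.5: −2.12 and −2.51

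The number of visits does not enter the formula. Deleting the Day-0 rows and changing nothing else would leave the bias as it is.

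**Day-0 score as covariate.** Remaining slope: c × (1 − ρ) / (1 − r²ρ). For r = −0.3:
- ρ = 0.5: −1.27 × 0.5 / 0.955 = −0.67, or 52% of the bias
- ρ = 0.7: −1.51 × 0.3 / 0.937 = −0.48, or 32% of the bias

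The correction is partial because one score measures the stable level with error.

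**Use by post-baseline interaction, Day 0 kept.** The spurious slope is c at Day 0 and c afterwards, so the interaction is c − c = 0 when the entry difference is stable.

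**Simulation** (3,000 studies per setting, true effect zero). Cells show the mean slope and the share of 95% intervals excluding zero. The level model includes age, sex, interval time and visit. The two alternatives were run without interval time.

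| r | ρ | SAP level model | Day-0 covariate | Use × post-baseline |
|---|---|---|---|---|
| 0 | 0.5, 0.7 | −0.01 (5%) | 0.00 to 0.01 (about 5%) | 0.01 (5%) |
| −0.3 | 0.5 | −1.28 (37%) | −0.67 (18%) | 0.00 (about 5%) |
| −0.3 | 0.7 | −1.48 (39%) | −0.48 (14%) | 0.00 (about 5%) |
| −0.5 | 0.5 | −2.13 (78%) | −1.21 (45%) | 0.00 (about 5%) |
| −0.5 | 0.7 | −2.50 (82%) | −0.91 (33%) | 0.00 (about 5%) |

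Leaving out interval time or the visit terms barely changes the level-model column. Day-0 scores analysed alone give the same slopes (−1.27 to −2.50), which are associations with use that had not yet occurred. A second, simpler simulation (4,000 studies per setting, no interval covariate) gave 42% to 45% for the level model at r = −0.3 and 15% to 20% with the Day-0 covariate. At r = −0.2 the figures were 20% to 21% and 9% to 11%.

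**Precision** (approximate SE per SD of use, n = 40, residual variance over n). Let B = 36ρ and W = 36(1 − ρ).
- Level model, √[(B + W/5)/40]: 0.73 at ρ = 0.5, 0.83 at ρ = 0.7
- Interaction, √[1.25W/40]: 0.75 and 0.58
- Day-0 covariate, √[(B − B²/36 + W/4)/40]: 0.58 and 0.51

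**Other reading of average use.** If use is a per-interval value, zero at Day 0, and the model has a random intercept, the spurious slope is −0.12 to −0.37 per SD of that variable across r = −0.3 and −0.5, and 6% to 12% of intervals exclude zero.

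**The case against.** The strongest reply is that the SAP claims only an association, labels every analysis exploratory, and belongs to a 40-person feasibility study whose primary outcome is adherence. That limits the severity. It does not remove the problem: the SAP ties the exploratory label to the number of outcomes, which is a matter of multiplicity, and the estimates will still be reported with 95% intervals.

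A second reply is that the SAP does not define the period for average use, and on a per-interval reading the bias is small. This stands as a real ambiguity. It is the less natural reading, because interval meditation time is already listed as a separate covariate and the two would nearly duplicate each other.

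Third, the size and sign of the bias come from an assumed SD, ρ and r. That is correct. The mechanism does not depend on them, but the figures do.

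A reader might infer more than the documents support:
- That lighter users are the study's only comparator. They are the only concurrent one. Secondary hypothesis (a) and the Protocol also name each participant's own baseline; the gap is that this model does not estimate that contrast.
- That including Day 0 is the error. Day 0 is what allows the entry difference to be separated out; the missing piece is the baseline or change term. Nor do the documents place every Day-0 questionnaire before the first demonstration session; only the LASA is expressly timed before treatment. One session could hardly create an association with 12-week use.
- That this model tests the Protocol's opening hypothesis or Aim 2. That hypothesis concerns resilience, which the SAP models separately, and Aim 2 concerns time in active and calm brain states. Both links are loose.

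**Conclusion.** The point holds for the stress and sleep model, with average use read as one value per person. The use coefficient then carries in full any stable entry difference between heavier and lighter users, and the model does not match secondary hypothesis (a). At r = −0.3, SD 6 and ρ of 0.5 to 0.7, with no true effect, this gives about −1.3 to −1.5 stress points per SD of use, with roughly 37% to 45% of intervals excluding zero against a nominal 5%. A positive r would reverse the sign. No separate figure is given for sleep; the same formula applies with that scale's SD.

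This is worth correcting but of lower severity, because it does not touch the adherence outcome. No version of the model yields a causal device effect, since workload and similar factors can drive use and stress together over time.

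**What to change.** Amend the SAP wording; every variable is already collected.

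1. Define the period over which use is averaged. With a 12-week average, 70 of the 84 days fall after Day 14 and 54 after Day 30, so the definition matters for the early visits as well.
2. Keep Day 0 in the outcome vector and make the interaction of average use with post-baseline visit (change from baseline by amount of use) the reported estimate.
3. Alternatively, model post-baseline scores with the Day-0 score as a covariate, and state that this only partly removes the bias (residual about −0.5 to −0.7, with 14% to 20% of intervals excluding zero, under the r = −0.3 assumptions).
4. Say whether interval meditation time stays in the model. It is zero before use begins and rises with average use afterwards, so it would overlap with the interaction term and change its meaning.
5. Report the correlation of Day-0 stress and sleep with later use.

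Costs: the interaction is less precise than the covariate version (SE about 0.75 against 0.58 at ρ = 0.5, and 0.58 against 0.51 at ρ = 0.7). The covariate version loses participants with no post-baseline score. Time-varying confounding remains under both, so the result should still be described as an exploratory association.

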## Research Question and Aims

**Hypothesis:** Healthcare providers (HCP) often deal with patients who are experiencing a variety of ailments, symptoms, and infections at the time of the face-to-face visit. There is an inherent stress that exists when one realizes the life of another being rests in their hands and capabilities. In addition, whereas the risk of contracting diseases in the course of caring for others has always existed, it has never been more evident than during this time of the Covid19 pandemic. The stress of caring for others while worrying about the potential ramifications of their care management decisions and the possibility of contracting Covid19 and inadvertently passing said disease to others (friend and family included) has significant physical and mental health ramifications for HCP. Whereas it has been touted that mindfulness can be a benefit to physicians in the front line, little guidance exists as to how this can be learned and practiced by HCP during such a busy time with little respite. We postulate that using a novel biofeedback-assisted meditation device (Muse-S™) often during the workday can provide mindfulness training to increase calm state brain activity in physicians during a busy practice in the midst of a pandemic. We hypothesize that the greater amount of time the HCP uses this tool, the greater amount of resilience s/he builds, providing needed mental support.

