### **Aims, purpose, or objectives:**

1. To study the feasibility of HCP using a wearable brain sensing wellness device (Muse-S™) during a time of increased workload, patient volume and stressors.
2. To assess the association between duration of active state and calm state as measured by the wearable brain sensing wellness device (Muse-S™), and quality of life (QOL), subjective stress, sleep and resilience.

The primary outcome will be the adherence to the Muse-S™ by summarizing the frequency of use and duration of use each time it was accessed.

The secondary outcomes will include:

- change in stress score over time
- measures of QOL, resilience and coping score in HCP at specific time points post baseline.

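### The stress/sleep model adjusts average Muse-S time for interval total meditation time, so its coefficient may not be the use-outcome association; Day 0 and Day 180 have no planned use value

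*SAP*

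**What the plan says.** The SAP, under Data Analysis Plan, states the purpose of the stress and sleep model as "to estimate the association between the average of time spent using the Muse-S™ with the stress and sleep level outcome". On which assessments enter it, the same sentence says: "A linear mixed model with repeated measures for each time point that stress and sleep were taken will be utilized". The covariates come in the sentence after: "Age, sex, and the total amount of meditation time at each interval will also be adjusted for in the model". Neither the unit of the average (session, week, interval or whole treatment period) nor the interval is defined.

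The Protocol does not settle the unit. Under Aims, the adherence outcome is obtained by "summarizing the frequency of use and duration of use each time it was accessed", while Aim 2 concerns "the association between duration of active state and calm state as measured by the wearable brain sensing wellness device". The Hypothesis is about amount of use, but for resilience: "the greater amount of time the HCP uses this tool, the greater amount of resilience s/he builds". Under Methods, participants may shorten sessions: "If they are short on time, they can break up the 10 minutes and do shorter meditations". The description of the meditation types allows guided sessions without the headband.

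On timing, the schedule scores stress and sleep at Days 0, 14, 30, 90 and 180. The Methods list "Frequency and duration of use from baseline to month 3 (end of treatment" as the period over which use is assessed, and the SAP summarises use over 12 weeks.

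**The concern.** Average use and interval total use are both computed from the same logged session minutes. With both in one model, the coefficient on the average answers this question: among people with the same minutes in this interval, how does the outcome differ with average use? That is generally not the association the SAP sentence sets out to estimate. With the average undefined, two analysts could follow the SAP faithfully and report different quantities under one label.

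This is the only model in the SAP that contains use. LASA, resilience, coping and cognition are modelled for change over time. A small average-use coefficient could therefore be read as no link between use and stress or sleep when the total-time term has taken up the link.

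The timing gap is separate. The model takes every stress and sleep assessment, so Day 180 qualifies, but no use value is planned for Days 90 to 180. At Day 0 no use has yet occurred.

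**Working it through.** **Inputs from the documents.** 40 participants; requested use 4 x 10 = 40 min/week; assessments at Days 0, 14, 30, 90 and 180. Treatment intervals are therefore 14, 16 and 60 days, or L = 2.00, 2.29 and 8.57 weeks. No SD, effect size or power figure is given, so there is no planned figure to reproduce.

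**Notation.** T = minutes in an interval; R = T/L = weekly rate; A = (sum of T)/(sum of L) = person average over treatment.

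**Step 1: algebra.**
- *Exposure R.* R = T/L, so R and T correlate at 1.0 within each visit. They separate only because the intervals differ in length.
- *Exposure A.* Let the between-person slope be bB and the within-person slope bW. Then bB·A + bW·(R − A) = (bB − bW)·A + bW·R. Adjusting A for current use turns its coefficient into roughly a between-minus-within contrast. This is only approximate here because the plan adjusts for T, not R.
- *Effect runs through T.* The T term carries the whole effect and the coefficient on A is 0, whatever the SDs. Without T, at a slope of -1 per 100 min, 10 min/week is worth 20.0, 22.9 and 85.7 min in the three intervals. The mean is 128.6/3 = 42.9 min, giving -0.43. With a Day 0 row of zero use it is 128.6/4 = 32.1 min, giving -0.32.

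**Step 2: simulation, exposure A.** Assumed, not from the documents: between-person SD 5, residual SD 4, log-SD of use 0.58 between and 0.4 within persons, and a visit term. True slope -1 (per 10 min/week for rates and averages, per 100 min for interval minutes).

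| Effect runs through | Day 0 row | With total time (as planned) | Without |
|---|---|---|---|
| Interval minutes | excluded | 0.00 | -0.43 |
| Interval minutes | included | 0.00 | -0.32 |
| Weekly rate | excluded | -0.55 | -0.93 |
| Weekly rate | included | -0.31 | -0.70 |
| Person average | excluded | -1.00 | -1.00 |
| Person average | included | -0.57 | -0.75 |

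For the weekly-rate effect the share kept is 0.55/0.93 = 59% (Day 0 excluded). It ranges from 27% to 91% as the log-SDs vary over 0.4-0.8 between and 0.2-0.6 within persons. The SAP names no visit term; without one the 59% becomes 83%, and the interval-minutes result stays at 0.00.

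**Step 3: other definitions.**
- *Interval weekly rate (Day 0 excluded).* For a weekly-rate effect the slope is -1.00 with and without total time, but the SE rises from 0.157 to 0.219 (0.219/0.157 = 1.4-fold). For an interval-minutes effect it is 0.00 against -0.43.
- *Session length.* A second simulation assumed about 4 sessions/week (SD 1.5), 10 min/session (SD 3), person SD 5, residual SD 3 and a slope of -0.1 per min/week. One extra minute per session should give about 4 x -0.1 = -0.4. The model gave -0.418 without total time and -0.196 with it.
- *Scale against noise.* In that second simulation at 40 participants, the 12-week-average coefficient moved from -0.089 (SE 0.038) to -0.044 (SE 0.041). The shift of 0.045 is about one SE.

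**Step 4: Day 180.** With minutes per week as the only exposure, Day 0 excluded and true slope -1:
- coding Days 90-180 as zero use gives -0.94 if 25% of participants continue and -0.87 if 50% do. These errors of 0.06 and 0.13 are within one SE (0.135), and there is no bias if nobody continues;
- carrying the last interval forward gives -0.79 if nobody continues;
- dropping Day 180 gives -1.00 (SE 0.156), and using logged minutes gives -1.00 (SE 0.12-0.13).

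**The case against.** The strongest reply is Aim 2. If the time being analysed is calm- or active-state time, total meditation time is a sensible control for how long the person was recorded, and removing it would harm the analysis. This stands as a condition on the point. The SAP wording refers to time using the device and does not establish that reading, but the documents do not exclude it. Session length at equal total time is likewise a coherent question, since sessions may be split.

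Second, the Hypothesis on amount of use concerns resilience, so it cannot serve as the benchmark for stress and sleep. That is right. The benchmark is the SAP's own sentence, read with Aim 2.

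Third, average plus time-varying use resembles a within/between split, which is a legitimate model, and the SAP promises estimates with confidence intervals, so the total-time coefficient need not be hidden. This is partly right. The plan does not present the two terms as a split, and nothing tells the reader which coefficient carries the association.

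Fourth, the zero results assume an effect that runs wholly through the covariate. True: they show what can happen, not what will.

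A reader might go further and infer that the planned coefficient must be near zero, or that the model cannot be fitted. The documents support neither. No mechanism is stated, some cases show no change, and unequal intervals keep even R and T separable. Nor do they show that use after Day 90 goes unrecorded. Under Server Data, any session is uploaded and deletion comes only at the end of the study. A 12-week average would also be defined at Day 180; it is the interval total that has no planned value.

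**Conclusion.** The point holds conditionally. If the average means amount of use, the planned coefficient is average use at fixed interval total, and it equals the use-outcome association only under particular combinations of definition and mechanism. It can be near zero, attenuated, unchanged, or unbiased with an SE about 1.4 times larger. The change of meaning follows from the text and algebra; every size rests on assumed SDs and, for the attenuation figures, on a visit term the SAP does not name, so the figures are illustrative.

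The missing use values for Day 0 and Days 90-180 follow directly from the schedule and the stated assessment period.

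The importance is minor to moderate. The primary outcome, adherence, is descriptive and unaffected, and the SAP labels all analyses exploratory. That label deals with the number of outcomes; it does not make an undefined coefficient interpretable. It would overstate the case to infer that the study will miss a benefit of use, or that adjusting for total time is wrong whatever the exposure: the first needs a mechanism the documents do not state, and the second fails under the Aim 2 and session-length readings.

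**What to change.** In the SAP:

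1. Name one amount-of-use exposure for the main stress/sleep model, with unit and window: for example minutes per week in the interval ending at each post-baseline assessment, or the 12-week average. State whether sessions without the headband count.
2. Adjust for age, sex, visit and baseline score, with post-baseline rows only, which settles Day 0. Do not also adjust for total meditation time.
3. Report the other use measure, or a within/between-person split, as a sensitivity analysis.
4. Keep total meditation time as a covariate only if the exposure is declared to be calm- or active-state time or session length. In that case report the total-time coefficient as the use-outcome association.
5. Either limit the use-outcome model to assessments through Day 90 and report Day 180 descriptively, or extract session logs through Day 180 before the end-of-study deletion.

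The cost is SAP wording plus an optional longer log extract; session times and durations are already uploaded. Average use at equal total time would no longer be estimated in the main model. Neither exposure captures every mechanism. In the Step 2 simulation, minutes per week alone recovers only -0.33 of a person-average effect of -1 (Day 0 excluded; -0.49 with baseline score as covariate). The 12-week average alone recovers -1.00, but it relates the Day 14 and Day 30 scores partly to later use. Stopping at Day 90 costs some precision (SE 0.156 against 0.12-0.13 with logs). The result remains an association, because participants choose how much to use the device.
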